## Department of Medicine/Endocrinology

Email:

Phone:

38        **Abstract:**  
39  
40        Basal-bolus insulin therapy is recommended for patients with poorly controlled type 2  
41        diabetes and HbA1c >9%. However, basal-bolus insulin is labor intensive and associated with  
42        increased risk of hypoglycemia, glycemic variability, weight gain and poor compliance. Thus,  
43        there is a critical need for a simpler treatment regimen that could overcome these limitations.  
44        IDegLira, a fixed-ratio combination (FRC) therapy consisting of insulin degludec and liraglutide,  
45        is an attractive option for this population given its proven benefits on glycemic control, weight  
46        and compliance. *Accordingly, we propose a prospective randomized controlled trial comparing*  
47        *IDegLira and basal-bolus insulin therapy in achieving glycemic control (efficacy end-point), while*  
48        *preventing hypoglycemia and reducing glycemic variability and weight gain (safety end-point) in*  
49        *patients with uncontrolled T2D and HbA1c between ≥ 9-15%.* This study aims to show that a  
50        simpler regimen using a novel FRC agent (IDegLira) can improve glycemic control, decrease  
51        hypoglycemia, reduce the burden of diabetes care, and improve satisfaction/adherence in  
52        patients with poorly controlled T2D with HbA1c between ≥ 9-15%. This open-label, treat-to-  
53        target, two-arm parallel, controlled trial will randomize (1:1 ratio) patients with T2D and HbA1c ≥  
54        9%, treated with oral antidiabetic agents and/or basal insulin therapy (TDD ≤50 units), to  
55        IDegLira or basal-bolus insulin for 26 weeks. We will recruit a total of 150 patients from  
56        participating institutions. We anticipate recruiting 3-4 patients per week for a total recruitment  
57        period of approximately 12 months.

58

59      **BACKGROUND:**

60

61      Extensive literature from landmark studies have shown that persistent hyperglycemia is  
62      associated with short- and long-term complications. The UKPDS study, the largest study in  
63      patients with type 2 diabetes, showed that intensive glycemic control can reduce the risk of  
64      microvascular complications. Sustained hyperglycemia, also known as glucotoxicity, leads to  
65      progressive loss of beta-cell function and is considered a key pathophysiological process in the  
66      development of T2D. Patients with severe hyperglycemia may respond poorly to oral anti-  
67      diabetic agents (OAD) alone initially and frequently require insulin to achieve glycemic targets  
68      . Current guidelines recommend to initiate therapy with basal insulin and progressively step-  
69      up to basal-bolus insulin in patients with high HbA1c >9%, particularly if symptomatic or with  
70      catabolic symptoms.

71      Basal-bolus insulin regimen increases the risk of hypoglycemia, weight gain and  
72      glycemic variability, which are limiting factors in achieving glycemic targets. Basal-bolus  
73      insulin regimen is also labor intensive and often requires multiple daily injections, further  
74      increasing the burden of diabetes care and decreasing patient adherence. In contrast,  
75      simplified treatment plans may improve adherence, leading to glycemic targets  
76      achievement. Thus, there is a critical need for simpler regimens that could overcome  
77      clinical inertia, improve patient adherence, and decrease glycemic variability in patients with  
78      poorly controlled type 2 diabetes. With the advent of continuous glucose monitoring (CGM), we  
79      have recognized that hypoglycemia and glycemic variability are common events in many  
80      patients, even in patients with well-controlled T2D. Despite large data supporting the efficacy  
81      and safety of combination therapy with basal insulin and GLP1-RA -including fixed-ratio  
82      combination (FRC) agents; no previous studies have compared the efficacy and safety of  
83      IDegLira in patients with very high HbA1c vs the standard-of-care with basal-bolus insulin  
84      regimen. *Accordingly, this prospective randomized control trial will compare IDegLira to basal*  
85      *bolus insulin regimen in achieving glycemic control (efficacy end-point), while reducing*  
86      *hypoglycemia, glycemic variability and weight gain (safety end-point) in patients with*  
87      *uncontrolled T2D and HbA1c ≥9%.*

89 **SPECIFIC AIMS:**

90 **Specific Aim 1:**

91 ***1. To determine whether treatment with IDegLira will result in similar improvement in***  
92 ***glycemic control, as measured by change in HbA1c (non-inferiority limit of 0.4%),***  
93 ***compared to treatment with basal-bolus insulin regimen in patients with poorly***  
94 ***controlled T2D (HbA1c  $\geq$ 9-15%).***

- 95 - Primary outcome: change in HbA1c from baseline after 26 weeks of treatment with  
96 IDegLira vs basal-bolus insulin (with metformin, unless contraindicated).
- 97 - **Hypothesis:** After 26 weeks of treatment, IDegLira will result in similar improvement in  
98 glycemic control compared to basal-bolus insulin therapy.

99 **Specific Aim 2:**

100 ***2. To determine whether treatment with IDegLira will result in lower rate of***  
101 ***hypoglycemic events and less glycemic variability (superiority), as measured by***  
102 ***continuous glucose monitoring (CGM), compared to basal-bolus insulin in patients***  
103 ***with T2D and HbA1c  $\geq$ 9-15%.***

- 104 - Patients with poorly controlled T2D randomized to IDegLira or basal-bolus (with  
105 metformin, unless contraindicated) will have a one-week blinded CGM study performed  
106 during follow-up visits at 1, 12, and 26 weeks as well as 8-point self-monitored blood  
107 glucose (SMBG). CGM will allow better detection of hypoglycemic events, particularly  
108 asymptomatic and nocturnal hypoglycemia. It will also provide critical information on  
109 time in glycemic range and glycemic variability.
- 110 - **Hypothesis:** IDegLira will result in less hypoglycemia and glycemic variability  
111 compared to basal-bolus insulin regimen.

112 **Specific Aim 3:**

113 ***3. To determine whether treatment with IDegLira will result in improved patient***  
114 ***satisfaction compared to treatment with basal-bolus in patients with T2D and high***  
115 ***HbA1c ( $\geq$ 9-15%).***

- 116 - Patients with poorly controlled T2D randomized to IDegLira or Basal-Bolus will  
117 complete the Diabetes Treatment Satisfaction Questionnaire (DTSQ) and Treatment-  
118 related impact measures for diabetes (TRIM-D) survey during follow-up visits.
- 119 - **Hypothesis:** Use of IDegLira is associated with higher patient satisfaction and  
120 adherence compared to a multiple-daily injection regimen with basal-bolus insulin.

122 **CURRENT STATUS OF WORK IN THE FIELD**

123 **Epidemiology and treatment of patients with poorly controlled T2D and HbA1c >9%**

124

125

126       Based on NHANES data from 2007-2010, up to   135   with Diabetes: US and Emory Data

127   12.6% of patients with diagnosed diabetes (18.8 millions)   136

128   have an HbA1c >9%. In the Emory Health Care system   137

129   the largest academic health system in Georgia, over   138

130   64,000 patients have a diagnosis of diabetes, with ~16%   139

131   having an HbA1c>9% (Figure 1). The evidence on the   140

132   management of patients with T2D and very high HbA1c   141

133   very limited, with most studies excluding patients with   142

134   HbA1c > 10%. Figure 1. HbA1c Distribution in Patients   143

135   144

[figure not shown]
136   145

137   146

138   147

139   148

140   149

150       In a recent multi-national study of insulin-naïve patients with T2D, treated with or without  
151   oral agents, showed that only ~40% of patients with HbA1c > 9% were started on basal insulin.  
152   Moreover, the study showed that only 20.9% of such patients achieved HgA1c target (< 7%) at 3  
153   months after initiating basal insulin, indicating a need for coverage of prandial-related  
154   hyperglycemic excursions. Notably, failure to achieve HbA1c targets at 3 months was associated  
155   with an increased risk of not achieving HbA1c targets at 24 months, with < 30% of patients  
156   achieving glycemic targets. This study suggests that providers delayed initiation of basal insulin  
157   as recommended by national guidelines, and frequently failed to intensify therapy to cover  
158   prandial-related hyperglycemic excursions. A recent study in ambulatory patients with T2D and  
159   high HbA1c (>10%) on metformin and sulfonylurea treatment, randomized patients to  
160   combination (COMB) therapy with exenatide plus pioglitazone vs basal-bolus insulin regimen.  
161   COMB provided greater HbA1c reduction at 6 months, with significantly less weight gain.  
162   However, the rates of hypoglycemia were unusually high, up to 56% and 83% in COMB and BB,  
163   respectively. Our group recently validated the efficacy of a hospital discharge algorithm based  
164   on the admission HbA1c. Among those patients with high admission HbA1c> 9% (n: 81), 54  
165   were discharged on basal-bolus insulin regimen. Mean admission HbA1c of 11.1% decreased to  
166   8.8% and to 8.0% after 4 and 12 weeks of hospital discharge (p<0.01), respectively. However, up  
167   to 44% of patients had hypoglycemia (BG < 70 mg/dl) during follow-up. Thus, there is a critical  
168   need for effective but safe and simpler anti-diabetic regimen for this high-risk population.

169

170

171 **“Standards-of-Care” for Patients with Severe Hyperglycemia**

172       Based on expert consensus, the American Diabetes Association recommends “dual  
173       therapy” for patients with HbA1c >9% to achieve glycemic targets faster than with “sequential  
174       therapy” after 3 months of not achieving such targets. Based on historical availability and with  
175       no hierarchical preference by the ADA, dual therapy includes metformin and any of the following  
176       agents: sulfonylureas (SU), thiazolidinedione (TZD), glinides (GLN) dipeptidyl peptidase-4  
177       inhibitors (DPP-4), SGLT-2 inhibitors, GLP-1 agonists and basal insulin. Similarly, the American  
178       Association of Clinical Endocrinologists (AACE) based on expert consensus recommends the  
179       addition of insulin in patients with HbA1c >9% if symptomatic, or on maximum doses of dual  
180       therapy. Moreover, in patients with HbA1c >8% on dual therapy and/or long history of diabetes,  
181       AACE suggests that the addition of insulin will more likely achieve glycemic targets over adding  
182       a third agent. It was also suggested that the addition of GLP-1 to dual oral therapy may  
183       similarly help achieving glycemic targets, but still many patients will require insulin in this  
184       scenario. In patients with HbA1c > 10%, or blood glucose > 300 mg/dl, and/or symptomatic  
185       hyperglycemia (polyuria or polydipsia) and catabolic symptoms (ketosis and weight loss), the  
186       ADA recommends “combination insulin injectable therapy”. This regimen includes: basal-bolus  
187       insulin or basal plus GLP1-RA or pre-mixed insulin. Notably, recommendations from national  
188       guidelines in this area are mostly based on expert consensus and the notion that “dual injectable  
189       therapy” for patients with HbA1c >9% may achieve glycemic targets faster than with “sequential  
190       therapy” after re-evaluation every three months, rather than based on strong clinical trials  
191       evidence. Unfortunately, the evidence is very limited in patients with T2D and v e r y high  
192       HbA1c, with most studies excluding patients with HbA1c > 10%.

193  
194       In clinical practice, many patients with uncontrolled T2D and HbA1c > 9% are started on  
195       basal insulin, followed by dose up-titration and addition of prandial insulin (basal bolus)–in  
196       concordance with national guidelines. Intensive insulin therapy, by either continuous  
197       subcutaneous insulin infusion (CSII) or multiple daily insulin injections (MDI), early in the  
198       disease course of patients with T2D results in rapid glycemic control within days, suggesting  
199       that avoiding the negative effects of long-term exposure to hyperglycemia may prevent further  
200       beta-cell failure. However, the basal bolus regimen increases the risk of hypoglycemia and  
201       weight gain, which are well-recognized limiting factors to achieve glycemic targets. More  
202       importantly, basal bolus regimen is labor intensive and increases the burden of diabetes care,  
203       number of injections per day, which may lead to poor patient adherence, increase re-  
204       admission rates, and increased risk of hypoglycemia. Studies comparing GLP1-RA therapy  
205       vs thrice-daily bolus insulin added to basal insulin plus oral agents have found similar HbA1c

206 reduction accompanied by weight loss compared to weight gain in basal-bolus insulin  
207 regimen. GLP1-RA therapy was also associated with better patient satisfaction and better  
208 quality of life. *Indeed, the combination of basal insulin and GLP1-RA is an attractive and*  
209 *simpler option for many patients with uncontrolled diabetes – ideally in a single daily injection*  
210 *from a fixed-ratio combination agent.* Moreover, there is evidence suggesting that GLP-1  
211 agonist therapy may preserve beta-cell function. Based on data from meta-analysis and  
212 randomized studies, some authors favor this combination over basal-bolus insulin in  
213 patients with uncontrolled T2D on basal insulin.

214

215 **Combination of basal insulin and GLP-1 agonists – fixed-ratio combination agents**

216        The combination of basal insulin and GLP1-RA therapy offers a complementary  
217 mechanism to target the main physiologic defects in T2D, by addressing fasting and prandial  
218 hyperglycemia. GLP1-RAs decrease post-prandial glycemic excursions and complement  
219 basal-insulin therapy by enhancing endogenous insulin responses in a glucose-dependent  
220 manner, inhibiting glucagon secretion, slowing gastric emptying and promoting satiety. This  
221 combination has been shown to provide better glycemic control, less hypoglycemia, less weight  
222 gain, and reduce glycemic variability compared to basal bolus therapy or GLP1-RA  
223 alone. IDegLira is a novel fixed-ratio combination of degludec 100 u/ml and liraglutide  
224 3.6 mg in a pre-filled pen. IDegLira has been shown to improve glycemic control, with lower risk  
225 of hypoglycemia, less weight gain, and better patient satisfaction compared to basal-bolus or  
226 stepped-up basal therapy. Pharmacokinetics studies showed that IDegLira provided  
227 coverage over the 24-hours interval at steady levels. In the recent DUAL V trial, IDegLira  
228 resulted in greater HbA1c reduction, weight loss and less hypoglycaemia, compared to up-  
229 titration of insulin glargine in patients with T2D with HbA1c 7-10%. More recently in the DUAL  
230 VII trial, patients with HgA1c 7-10% randomize to IDegLira had similar HbA1c reduction, but  
231 with an 89% reduction in the rate of severe or confirmed symptomatic hypoglycemia and weight  
232 loss compared to basal-bolus insulin. Thus, IDegLira is an attractive and option for patients  
233 with severe hyperglycemia, due to potent HbA1c reduction, lower hypoglycemic risk, and  
234 flexibility of once-daily administration, compared to up to five injections per day in basal-bolus  
235 regimen. However, no previous studies have compared the efficacy and safety of IDegLira in  
236 patients with high HbA1c >9-15%.

237

238

239 **SIGNIFICANCE AND INNOVATION:**

240                   The proposed study will test three innovative questions in patients with poorly controlled  
241                   T2D and HbA1c  $\geq 9\%$ : 1) whether IDegLira, a novel FRC of degludec and liraglutide, results in  
242                   similar glycemic control, 2) less hypoglycemia, less glycemic variability and less weight gain  
243                   compared to a basal-bolus, and 3) whether IDegLira results in better patient satisfaction and  
244                   treatment adherence compared to a more complex multiple-daily insulin injection regimen. If  
245                   successful, this study will show that a once-a-day simpler regimen using IDegLira can improve  
246                   glycemic control, decrease hypoglycemia, improve satisfaction and decrease the burden of  
247                   diabetes care, which in turn will improve patient adherence. Since improvements in HbA1c  
248                   strongly correlate with a reduction in the risk of microvascular and macrovascular complication,  
249                   improved glycemic control with a simpler regimen like IDegLira have the potential to reduce the  
250                   burden of complications associated with T2D. In addition, we will perform professional/blinded  
251                   CGM at weeks -1, 12 and 26 of follow-up. By incorporating CGM, we will improve our ability to  
252                   detect asymptomatic/unrecognized and/or nocturnal hypoglycemia and assess glycemic  
253                   variability compare to SMBG (standard-of-care). Since IDegLira therapy is expected to result  
254                   in less clinical significant hypoglycemia (defined as interstitial glucose  $< 54$  mg/dl), less  
255                   nocturnal hypoglycemia and less glycemic variability (as measured by MAGE, %CV or SD)  
256                   compared to basal-bolus, this simpler regimen could become the standard-of-care for patients  
257                   with uncontrolled T2D and HbA1c  $\geq 9\%$ .

258  
259                   **RESEARCH DESIGN and METHODS**  
260  
261

262                   **ENDPOINTS:**

263                   The **primary outcome** of the study is to determine the difference in change in HbA1c at 26  
264                   weeks of treatment to a non-inferiority limit of 0.4% between IDegLira and basal-bolus insulin  
265                   therapy.

266                   The **secondary outcomes** are to compare differences between IDegLira and basal-bolus  
267                   insulin therapy in any of the following measures:

[figure not shown]
- 268                   • Mean fasting and mean daily blood glucose (per 8-point SMBG profile)
- 269                   • Percent of patients with HbA1c  $< 7.0\%$  at 26 weeks and hypoglycemia
- 270                   • Percent of patients reaching A1c  $< 7\%$  without weight gain and no hypoglycemia”  
271                   (responder’s rate)
- 272                   • Percent of patients reaching A1c  $< 7.5\%$  without weight gain and no hypoglycemia”
- 273                   • Percent of patients with A1c  $> 10\%$  and  $> 11\%$  that achieve A1c  $< 7.5\%$  and  $< 8\%$

- Percent of patients with HbA1c <7.0% at 26 weeks and no weight gain
- Percent of patients with HbA1c <7.0% at 12 weeks and no hypoglycemia
- Incidence of documented symptomatic hypoglycaemia, defined as an event with typical symptoms of hypoglycaemia accompanied by SMBG or CGM (<70 mg/dL and < 54 mg/dL) that occurs at any time of the day
- Incidence of asymptomatic hypoglycaemia, defined as no typical symptoms reported by the subject but detected by SMBG or CGM (<70 mg/dL and < 54 mg/dL)
- Incidence of severe hypoglycaemia, defined as severe cognitive impairment requiring assistance from another person
- Incidence of nocturnal symptomatic hypoglycaemia, defined as an event with typical symptoms of hypoglycaemia accompanied by SMBG or CGM <70 mg/dL and < 54 mg/dL that occurs between 00:00 and 05:59 hrs
- Incidence of nocturnal asymptomatic hypoglycaemia, defined as SMBG or CGM <70 mg/dL and < 54 mg/dl between 00:00 and 05:59 hrs
- Percentage of time below 70 mg/dL and <54 mg/dl as obtained by CGM
- Percentage of time in range (BG 70-180) as measured by CGM
- Glycemic variability, as measured by SD (standard deviation), %CV (coefficient of variance), Mean Amplitude Glucose Excursions (MAGE)
- Patient satisfaction and quality of life, as measured by the DTSQ and T R I M - D questionnaires
- Number of emergency room visits and hospital readmissions
- Change from baseline in total insulin dose (units/day)
- Number of treatment emergent AE

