**Assessments for Efficacy**

791 The primary outcome of efficacy will be determined by change of HbA1c from baseline  
792 after 26 weeks of treatment. HbA1c will be measured by the clinical laboratory of  
793 Grady Memorial Hospital and Emory University, a NGSP-certified laboratory. Subjects will  
794 complete an 8-point SMBG for at least 1 day before the CGM visits. We will also compare the  
795 time in target range (70-180) as detected by CGM, allowing us to assess glycemic control for > 7  
796 days with frequent testing (CGM and POC BG). We will compare the rate of "responders",  
797 defined as patients HbA1c  
798 <7.0% and no hypoglycemia at week 26.

799  
800

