### 866 **Subject Compliance**

867 Subject compliance will be assessed by monitoring of drug accountability. Subjects will be  
868 encouraged at every visit to adhere to the study medications and follow-up schedule. Unused  
869 trial medications will be compared with dispensed amount at each corresponding visit. If  
870 discrepancies are noted, the subject will be asked.

871  
872 **STATISTICAL CONSIDERATIONS:**  
873 **Sample Size Calculation**  
874       The primary outcome is the change in HbA1c from baseline after 26-weeks of treatment.  
875       The primary hypothesis is that HbA1c change is similar between the IDegLira group and the  
876       basal-bolus group. Given the data reported for the DUAL V study, we assume the HbA1c  
877       change from baseline has a standard deviation bounded above by 0.85 (%). We assume the  
878       margin of equivalence is 0.4 (%) and the true mean difference in the primary outcome is 0 (%).  
879       Given 57 subjects per study group, based on a one-sided, two-sample t-tests, we would achieve  
880       80% power to detect non-inferiority, with alpha (type-1 error) set as 0.05. Accounting for 20%  
881       attrition rate of 20%, we need to recruit 75 subjects per group (150 in total).  
882  
883 **Statistical Methods**  
884       This is a randomized, open-label study. We will first compare the primary outcome (i. e.  
885       change in HbA1c from baseline to after 26 weeks of treatment) between the two study groups  
886       using nonparametric and parametric two-sample tests, such as Wilcoxon tests and t-tests. A  
887       logarithm transformation may be employed to make the data better conform to the normality  
888       assumption. We will apply standard variable selection and model checking procedures to decide  
889       the final model.  
890       Secondary outcomes include various measurements (related to glycemic control, quality  
891       of life, adverse effects, and etc.) collected at a single or multiple time points. For continuous  
892       outcomes measured a single time point (i.e. non-longitudinal outcome), we shall analyze them  
893       following the same strategy designed for the primary outcome. For discrete non-longitudinal  
894       outcome, we will use Chi-square (or Fisher's Exact) tests to compare them between the two  
895       study groups. This will be followed by logistic regression or Poisson (or Negative Binomial)  

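### The week-26 responder composite planned in the efficacy section is not in the secondary-outcome list, where the nearest item has the opposite hypoglycaemia condition and the responder label belongs to another composite

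*Combined protocol and SAP*

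**What the plan says.** Two parts of the protocol define outcomes that combine HbA1c below 7% with hypoglycaemia.

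- **ENDPOINTS, secondary outcomes.** The second item is the percentage of patients with HbA1c below 7.0% "at 26 weeks and hypoglycemia". The third is the percentage reaching A1c below 7% "without weight gain and no hypoglycemia". It carries the label "responder’s rate" and gives no week. Later items are "Percent of patients with HbA1c <7.0% at 26 weeks and no weight gain" and "Percent of patients with HbA1c <7.0% at 12 weeks and no hypoglycemia". A further item repeats the three-part composite with a cut-off of 7.5%.
- **Assessments for Efficacy.** The text begins "We will compare the rate of" responders, and defines them as patients with HbA1c "<7.0% and no hypoglycemia at week 26". There is no weight component.

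The Statistical Methods section gives generic methods for discrete outcomes (Chi-square or Fisher's exact test, then logistic or count regression). It defines neither composite.

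**The concern.** These are outcome definitions, so a programmer would build the analysis variables from them. Someone working from the ENDPOINTS list would tabulate patients who reached target and had hypoglycaemia. Someone working from Assessments for Efficacy would tabulate patients who reached target without it. Both could say that they followed the protocol.

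The word 'responder' adds to the problem. In the list it means a three-part composite that includes weight; in the efficacy section it means a two-part composite without weight. A responder rate in a report could therefore be either quantity, and a reader checking it against the protocol could not tell which was planned. At stake is the meaning of one or two secondary results, not the main conclusion of the trial.

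**Working it through.** **1. The plan's own figure.** The only computed figure in the plan is the sample size for the primary endpoint. The inputs, from Sample Size Calculation, are a "change from baseline has a standard deviation bounded above by 0.85" (%), a margin of 0.4%, a true difference of 0, one-sided alpha 0.05 and 80% power.

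- Normal approximation: n = 2 × (1.645 + 0.842)² × 0.85² / 0.4² ≈ 55.8, so 56 per group.
- Exact t-test power: 79.7% at 56 and 80.3% at 57, so the stated 57 is reproduced.
- Attrition: 57 / 0.80 = 71.25, so 72 per group. The stated 75 leaves 75 × 0.80 = 60 evaluable, which is conservative.

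None of this uses the responder definition, so correcting the wording changes no sample size.

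**2. The composites side by side.**

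| Where | HbA1c | Week | Hypoglycaemia | Weight | Called responder? |
|---|---|---|---|---|---|
| ENDPOINTS, item 2 | <7.0% | 26 | present, as written | – | no |
| ENDPOINTS, item 3 | <7% | not stated | absent | no gain | yes |
| ENDPOINTS, item 4 | <7.5% | not stated | absent | no gain | no |
| ENDPOINTS, weight item | <7.0% | 26 | – | no gain | no |
| ENDPOINTS, week-12 item | <7.0% | 12 | absent | – | no |
| Assessments for Efficacy | <7.0% | 26 | absent | – | yes |

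The last row matches none of the five above it. Item 2 has its cut-off and week but the opposite hypoglycaemia condition. Item 3 adds weight and has no week. Item 4 has another cut-off and adds weight. The weight item has no hypoglycaemia component. The week-12 item is at the wrong week.

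**3. What the literal wording would report.** Let p be the proportion at target at week 26 and h the proportion of those patients with hypoglycaemia.

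- Item 2 as listed: p × h
- Composite in Assessments for Efficacy: p × (1 − h)
- Sum of the two: p

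The two quantities are complements among patients at target and are equal only if h = 0.5. The protocol gives no value for p or h, so the following is purely an assumed range. For p from 0.20 to 0.40 and h from 0.20 to 0.60, the listed item runs from 0.20 × 0.20 = 4% to 0.40 × 0.60 = 24%. The planned one runs from 0.20 × 0.40 = 8% to 0.40 × 0.80 = 32%. The range shows only that the two cannot be interchanged; it predicts nothing about this trial.

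**4. What remains open once the negation is restored.** The list and the Definitions section use both <70 and <54 mg/dL, from SMBG or CGM, and define confirmed hypoglycaemia separately (a severe episode, or glucose <54 mg/dL). Neither responder definition says which applies. The window is also open: Table 1 records hypoglycaemia at every contact from week 1 to week 26, whereas on-treatment CGM is worn for about a week at weeks 12 and 26. Freedom from hypoglycaemia at week 26 could refer to the whole treatment period or to the last wear.

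**The case against.** The strongest reply is that the intended meaning can be recovered. Assessments for Efficacy states the negated form for the same cut-off and week. The week-12 item and both composites with weight are negated too, and Aim 2 expects less hypoglycaemia on IDegLira. One missing word, contradicted by every related item, is most plausibly a slip. A word lost when the PDF was converted to text cannot be excluded either, although nothing at that line shows it. This stands as an account of intent. It does not make the current text correct, and the conflict over the responder label would remain.

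Item 2 might also be read loosely as two separate outcomes: HbA1c below 7.0%, and hypoglycaemia. On that reading the week-26 responder composite is absent from the list altogether.

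A reader might infer two stronger things.

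- *That the list scores hypoglycaemia as success and so favours the arm with more of it.* The documents do not say this. The list introduces measures on which the arms are compared and assigns item 2 no direction. A higher percentage at target with hypoglycaemia can simply be read as worse.
- *That two definitions let the sponsor pick the reported one after seeing the data.* Both composites are already written down, and the efficacy section commits to comparing one of them. Any freedom to emphasise a secondary outcome comes from the long unranked list, and renaming one composite would not remove it.

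**Conclusion.** The point holds as an error in the definition of secondary outcomes. The week-26 two-part responder composite planned in Assessments for Efficacy is not in the ENDPOINTS list as written, the nearest listed item has the reverse hypoglycaemia condition, and 'responder' names two different composites. Followed literally, item 2 yields the complement of the planned endpoint among patients at target. That follows from the wording and needs no assumed rates.

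The size is limited. The primary endpoint, the non-inferiority margin and the 57 or 75 per group are untouched, and the protocol claims no confirmatory status for either composite. That a 'no' was dropped is an inference from the related items, so the sponsor should confirm it. The correction is worth making because it concerns what will be tabulated and costs little.

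**What to change.** Before outcome data are analysed:

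1. Confirm the intent of the second secondary outcome. If a negation was dropped, reword it as HbA1c below 7.0% at week 26 with no hypoglycaemia.
2. Use 'responder' for one composite only, with identical wording in ENDPOINTS and Assessments for Efficacy, and give the other a different name.
3. State the assessment week for the three-part composites (cut-offs 7% and 7.5%).
4. For every composite with a hypoglycaemia component, state which of the protocol's existing definitions applies (<70 or <54 mg/dL; SMBG, CGM or both) and over what observation window.

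The cost is a short text amendment. Items 1 to 3 are a few words each. Item 4 needs the sponsor to choose among definitions already in the protocol. No change to data collection, visits, sample size or the primary analysis follows.
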